7.4 Follow-up of AE

In case of detected AEs during the safety follow-up included in sessions' visits or phone calls, or if reported by the participant at any time (even after the study has concluded), the volunteer will be treated as appropriate. This may include discontinuation of study medication if necessary or provision of medical assistance. The event will be documented in the eCRF, and

study investigators will closely monitor the situation to ensure participant safety. If the required treatment for the adverse event is not compatible with the study protocol, the subject will be excluded from the study.

8. QUALITY CONTROL AND ASSURANCE

8.1 Data handling and record keeping/archiving

8.1.1 eCRF

The electronic Case Report Form (eCRF) is an investigator file, written for each study subject, which contains data necessary to the progress and the analysis of the study, including safety data.

In this study, the following data will be entered in the eCRF using the browser-based software REDcap :

- Review of inclusion and non-inclusion criteria (check boxes) *
- Demography: gender*, age*
- Concomitant medication(s)*
- weight*, size* and BMI*
- CYP2C19 genotype and phenotype
- For women: date of last menstrual cycle, contraception methods and pregnancy test result at each visit*
- Time of drug intakes*
- Time of venous and capillary blood samplings*
- Time of urine collections*
- SAE resulting in death and SUSARs*

All items followed by an asterisk will be entered directly in the eCRF and will be considered source documents.

Each page will include the subject's and visit's number as well as all the modifications dated and signed by the investigator.

8.1.2 Source data

eCRF will be considered as a source document for some data collected during the clinical trial (see section 7.1.1.). All phenotyping, genotyping and metabolomics data (including raw files)

will be available in an electronic version considered as a source document and stored on the secured server of HUG.

The section of the eCRF dedicated to the collection of medical data will also be integrated in the electronic medical records of HUG for each study subject to record all medical information, which could be of medical interest in case of further hospital admission out of the frame of this clinical trial. Other medical data (e.g. concomitant illness, medical history, known drug allergies, blood pressure and cardiac frequency) will be reported only in the electronic medical records of HUG for each study subject in order to evaluate their eligibility.

In case of monitoring, audit or inspection, the principal investigator will allow free access to these source data.

8.1.3 Documents storage and keeping

Data obtained during the study will be collected in the eCRF and/or in an electronic form (i.e. metabolomics and genetic data) and will be coded. The access will be secured and limited to the investigator and co-investigators or people authorized by the principal investigator to ensure the best confidentiality. Data of the study will be kept for 20 years after termination in a locked cabinet and/or a secured server with restricted access.

Subject's identification list will be kept for a sufficient time to allow the necessary medical follow-up when appropriate.

In the inform consent, the volunteers will be able to choose whether they want to know their genotypes/phenotypes or not. In case of particular (poor or ultrarapid) metabolism detection, volunteers will be informed on its potential impact in any future treatments.

8.2 Data Management

8.2.1 Data management system

All research subjects as well as biological samples will be coded. Data management will be performed on the secured server of HUG. The necessary precautions will be taken in order to ensure safety as described in section 7.2.

All the collected data are the property of the sponsor institution (HUG) and under the direct responsibility of the sponsor.

8.2.2 Data security, access and backup

Physical access to the data centres is logged and limited to authorized personnel using badge authentication. On a regular basis, vulnerability testing is performed to reduce potential exposure. Remote access to servers is limited to authorized personnel and connections are encrypted using SSH.

The internal HUG network is protected by multiple firewalls, proxy, reverse-proxy and antivirus solutions. Web servers operate under SSL (HTTPS) certifications, ensuring that Web connections are encrypted and secure.

Only people part of the investigation team, the sponsor team, the affiliated reviewers or auditors, as well as inspection authorities (Swissmedic) are given access to data.

Identification is made by a personnel ID and a password. Failure to provide the correct password after a limited number of attempts automatically disables the faulty account (protection against non-authorized attacks).

HUG infrastructure is under the responsibility of DSI ("Direction des Systèmes d'Information"). All exploitation, monitoring and backup operations are performed by DSI. Frequent backups are carried out using the best backup methods at HUG and are physically stored in a fire-proof safe.

8.2.3 Electronic and central data validation

Validation/review will be performed in parallel by appropriate people designated by the sponsor (co-investigators or other collaborators of the study). Up-to-date graphical and text reports, as well as descriptive statistics, will be made available to monitor data in real time.

8.3 Monitoring

Throughout the study, a monitoring will be realised to check the good application of the study protocol (see monitoring plan document).

8.4 Audit and inspection

In case of an audit or inspection by the regulatory authorities, the investigator will allow the authorized people to:

- visit the study local, installations and used material;
- meet all the people involved from near or far in the study;
- have a direct access to all the study documents and source data;
- see all the documents related to the study.

8.5 Confidentiality and data protection

Individual research subjects' data cannot legally nor ethically be made available to non-authorized people. Only the sponsor and other members of the study team, reviewers, auditors as well as inspection authorities are entitled to access such data.

No personal data or data that may easily identify subjects will be provided, with respect to the Swiss law on human research (Federal Act on Research involving Human Beings (HRA)) and its applicable ordinance OClin.

Along with the study number, each participant's biological sample and results data will be coded as the following : Patient's number as per the order of entrance in information session of the study + S (for session) + number corresponding to the session + the initial letter of the name of biological sample (urine, plasma, EV, or DBS), e.g. 12S3P, 3S2U, 23SEV, 7S1D. Venous blood samples relative to genotyping will be coded as the following : Patient's number as per the order of entrance in information session of the study + G (for genotyping), e.g. 12G, 3G, 7G.

At the end of the project, the entire database will be archived in a reusable format, including the subject's identification list. Archives encompass all raw data, transformed data, version history, and audit trails. Redeployment of the entire database is therefore possible whenever needed. An electronic copy of the archive will be stored in a coded form within the DSI infrastructure for a theoretical infinite period of time while all the measures necessary to maintain confidentiality are fully implemented. Data will be provided to authorized third parties as much as possible in non-proprietary formats (text, CSV, XML, PDF). However, some material will remain proprietary due to technical restrictions.

8.6 Storage of biological material and related health data

If participants sign the consent form that allows the reuse of data and biological samples, coded genetic data (blood) and other biological samples (plasma, DBS card and urine) will be stored. In that case, the 'biobank' storage procedure will be applied (see the file "règlement de la biobanque de l'étude biomarqueurs endogènes CYP2C19"). As mentioned earlier, an individual numerical code will be attributed to the biological samples from each volunteer, along with the study number. The coded samples will be stored in HUG at -80°C (except DBS cards, which are at -20°C) for an indeterminate period. If the blood and other biological samples were to be used for a study distinct than the present one, the investigator will ask the authorisation of the CCER by submitting a new protocol. Volunteers will be informed that they can withdraw their consent at any time and in that case, the samples will be destroyed.

9. STATISTICS

9.1 Number of subjects

The data from Bosilkovska et al.²⁴, Magliocco et al.³⁷, Zhou et al.¹¹ and Akasaka et al.⁴⁰ were used as a basis to measure the effect size required for our clinical study and the number of subjects required for each study group.

The software G*Power (version 3.1.9.7) was used to calculate the sample size for a two-sided paired samples t-test with a power ($1-\beta$) of 80% for the part 1 of the study. The Bonferroni correction was applied to adjust the p-value (α = type 1 error) in order to correct for multiple tests as it is the case in metabolomics analyses. Therefore, p-value is divided by the number of expected features, which was defined as 5000 according to the number of metabolic features obtained after data processing in the Magliocco et al. clinical study, of which metabolomics were used to prospect on CYP2D6 endogenous biomarkers³⁷. Consequently, the p-value used for the power calculation will then be $1 \cdot 10^{-5}$. Moreover, the effect size obtained for the statistical analysis and based on the Bosilkovska et al. trial is 1.156. After entering all these parameters, a sample size of 30 is measured, which implies that 30 healthy volunteers NMs-RMs-UMs are required to observe a difference between control session, inhibition session and induction session in the part 1 of the study.

For the second part of the study (validation of identified features in the first part), a semi-quantitative targeted analysis will be performed. In Zhou et al.¹¹ study, 14% of the total number of participants were PM individuals among all the study participants and were enrolled to confirm a statistical difference between CYP2C19 PMs and non-PMs in the pharmacokinetic of a single 20 mg dose of omeprazole. Moreover, 35% of the total number of patients were PMs in the study of Akasaka et al.⁴⁰ where PMs and non-PMs were compared to have a significant difference between serum EETs levels (potential endogenous biomarker of CYP2C19).

Following these data, 10 PM individuals i.e. 10 subjects, which is 25% of the total number of our subjects (mean proportion of Zhou et al. and Akasaka et al. studies when combined), will be recruited. Therefore, already genotyped healthy volunteers known from our database or new ones will be contacted and if achievable, 10 PMs and 30 NMs-RMs-UMs (40 in total) subjects will be recruited and compared to each other at baseline.

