Rationnel et Objectifs	
Le cytochrome P450 2C19 (CYP2C19) est l'enzyme responsable du métabolisme de médicaments fréquemment prescrits en clinique comme l'oméprazole, un antiacide inhibiteur de la pompe à proton (IPP), le citalopram, un antidépresseur inhibiteur sélectif de la recapture de la sérotonine (ISRS) ou le clopidogrel, un antiagrégant plaquettaire. Le CYP2C19 présente une importante variabilité interindividuelle de son activité dans la population générale due, notamment, à un fort polymorphisme génétique, avec une trentaine de variants alléliques identifiés à ce jour. Ceci résulte en cinq phénotypes distincts dans son activité : le phénotype métaboliseur lent (PM), le phénotype métaboliseur intermédiaire (IM), le phénotype métaboliseur normal (NM), le phénotype métaboliseur rapide (RM) et le phénotype métaboliseur ultra-rapide (UM).
 
Pour caractériser l'activité du CYP2C19, il existe différentes méthodes de phénotypage à savoir l'administration d'une substance-test métabolisée de manière spécifique par le CYP2C19 et la mesure de paramètres pharmacocinétiques, tels que l'aire sous la courbe (AUC), ou des ratios métaboliques entre les concentrations de la molécule-mère et de son métabolite. Les substances-tests les plus utilisées sont l'oméprazole (OPZ) et la méthénytoïne. Il est également possible de mesurer le phénotype de plusieurs isoformes des CYPs simultanément avec le phénotypage mixte, tel que le « Geneva cocktail » développé aux HUG. Ce dernier est composé de 6 substances-tests permettant de phénotyper simultanément 6 isoformes des CYPs, dont l'OPZ pour le CYP2C19.
 
Malgré une bonne tolérance de ce cocktail, certains patients peuvent être réticents à l'administration de médicaments de manière exogène et il n'est parfois pas possible de les administrer à certains patients (e.g. femmes enceintes, enfants, personnes âgées). Il convient par ailleurs d'attendre 2h après l'ingestion du « Geneva cocktail » avant d'effectuer la prise de sang, ce qui peut poser quelques contraintes pratiques en clinique.
 
L'utilisation de biomarqueurs endogènes de mesure de l'activité des CYPs permettrait ainsi de s'affranchir de ces obstacles et de rendre la pratique moins invasive et plus acceptable pour les patients. Une récente étude consacrée au CYP2D6 conduite au sein de notre service a permis d'identifier de nouveaux biomarqueurs endogènes pour cet isoforme, à savoir la solanidine, un alcaloïde aglycone très commun, et ses dérivés.
 
Le but de notre étude est d'identifier de nouveaux biomarqueurs endogènes pour mesurer (phénotyper) l'activité du CYP2C19 par métabolomique non ciblée.
 
Les volontaires sains seront stratifiés en deux groupes selon leur phénotype pour le CYP2C19 : les sujets PMs et NM-RMs-UMs. Les sujets IMs seront exclus afin d'observer des différences plus significatives au sein des deux groupes.
 
Objectif primaire :
 
 - Partie 1 : mise en évidence de potentiels substrats et/ou métabolites endogènes du CYP2C19 par métabolomique non ciblée sur des échantillons urinaires, plasmatiques et de vésicules extracellulaires dérivées du foie prélevés avant (baseline, session 1) et après administration répétée de fluvoxamine (inhibition enzymatique du CYP2C19, session 2) ainsi qu'après administration répétée de rifampicine (induction enzymatique du CYP2C19, session 3). - Partie 2 : identification des substrats et/ou métabolites endogènes du CYP2C19 parmi les composés mis en évidence dans la partie 1 par analyse semi-quantitative ciblée sur des échantillons urinaires, plasmatiques et de vésicules extracellulaires dérivées du foie des volontaires sains PMs et NM-RMs-UMs à la baseline (i.e sans administration préalable de fluvoxamine ou de rifampicine). 
Objectifs secondaires :
 
 - Identification des substrats et/ou des métabolites endogènes du CYP2C19 à l'aide de bases de données internes ou externes, par fragmentation en LC-MS/MS ou à l'aide de standards de référence. - Corrélation des concentrations plasmatiques et/ou urinaires et/ou de vésicules extracellulaires dérivées du foie d'un substrat et/ou un métabolite endogène du CYP2C19 avec le phénotype (ratio sanguin OH-oméprazole/oméprazole) et/ou le génotype du CYP2C19.

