2.8 Primary objective

The primary objective of this study is to identify and validate an endogenous substrate and/or metabolite of CYP2C19 activity using untargeted metabolomics and semi-quantitative targeted analysis in healthy volunteers.

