3. STUDY DESIGN

3.1 Overall description

The study will be an open-label study with a total of 40 healthy volunteers fulfilling inclusion/non-inclusion criteria, divided into 2 study groups: 10 healthy volunteers PMs and 30 NMs-RMs-UMs for CYP2C19 and participating in the three sessions:

- Session 1: urine and venous blood sampling. Determination of blood $MR_{OH-OPZ/OPZ}$ at baseline (no inhibitor administrated).
- Session 2: urine and venous blood sampling. Determination of blood $MR_{OH-OPZ/OPZ}$ after pre-treatment by fluvoxamine (strong inhibitor of CYP2C19).

- Session 3: urine and venous blood sampling. Determination of blood MR_{OH-OPZ/OPZ} after pre-treatment by rifampicin (strong inducer of CYP2C19).

Information:

At this step, the volunteer will have an interview with one of the co-investigators at the Clinical Pharmacology and Toxicology department and the study will be explained in detail. A sufficient time will be allowed before the inclusion session to guarantee sufficient time for reflection.

Inclusion:

Volunteers willing to participate and having signed the informed consent form (ICF) will undergo a clinical evaluation with a physician including liver and kidney tests, body mass index, genotyping (except if CYP2C19 genotype is already known) and a pregnancy test (women only). Women will be asked to use at least one physical contraceptive barrier (i.e. male or female condom, diaphragm, spermicide) throughout their study participation and 1 month after the end of the study, in addition of their hormonal contraception if applicable. In case of heavy menstrual bleeding, women will have to be recruited before or after their menstrual period to avoid the presence of blood in urine. In addition, all volunteers will be asked to avoid alcohol consumption on days of taking study drugs and 48 hours before day 0 of session 1. A volunteer code for the study will be assigned to each volunteer included in the study.

Only volunteers fulfilling the inclusion/non-inclusion criteria will be allocated to a study group.

Sessions course:

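### Part 2 is called validation, but its NM-RM-UM comparator is the set of session 1 samples used to select the features in part 1, so it is not independent confirmation

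*Protocol*

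**What the plan says.** Section 2.8 sets the primary objective as to "identify and validate an endogenous substrate and/or metabolite of CYP2C19 activity". Section 9.1 sizes part 1 with a "two-sided paired samples t-test with a power" of 80%, an effect size of 1.156 and a Bonferroni level for a number of features "which was defined as 5000". It concludes that "30 healthy volunteers NMs-RMs-UMs are required to observe a difference between control session, inhibition session and induction session".

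The same section then introduces part 2 as "validation of identified features in the first part" by semi-quantitative targeted analysis: 10 PMs and 30 NM-RM-UMs "subjects will be recruited and compared to each other at baseline". The synopsis objectives agree that part 2 uses samples of "volontaires sains PMs et NM-RMs-UMs à la baseline". (The synopsis method row numbers the genotype step as part 3.)

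There is a single cohort. Section 3.1 has "10 healthy volunteers PMs and 30 NMs-RMs-UMs for CYP2C19 and participating in the three sessions". No hold-out, split or second cohort is described. The only other validation is with recombinant enzymes and genotyped hepatocytes, a secondary objective in section 2.9. Section 9.2 plans FDR adjustment for the session contrasts and does not say which volunteers enter them.

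**The concern.** On section 9.1's account, the session 1 samples of the 30 NM-RM-UMs serve twice: as the control session when features are selected, and as the comparator when those features are validated. Suppose a feature has a high mean in those samples purely by chance. Session 2 then looks lower than baseline, and the PMs look lower than the NM-RM-UMs. Reduced levels under inhibition and in PMs are what one expects of a CYP2C19 metabolite, so the shared noise looks biologically coherent.

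What is at stake is the word in the primary objective. A confirmation step that shares data with the selection step does not reject chance selections at its nominal rate, and a reader of the trial report would take validated to mean that it does.

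**Working it through.** **Reproducing the plan's figure.** Noncentral-t power of a two-sided paired t-test, alpha = 0.05/5000 = 1e-5, effect size 1.156: 76.8% at n = 29 and 80.4% at n = 30. The stated 30 is reproduced.

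**Correlation of the two contrasts.** Let a feature's log intensity have variance σ² and correlation ρ between sessions within a volunteer. Under the null:

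- Part 1 contrast, mean(S1 − S2) over 30 NM-RM-UMs: variance 2σ²(1 − ρ)/30.
- Part 2 contrast, mean S1 of 30 NM-RM-UMs minus mean S1 of 10 PMs: variance σ²(1/30 + 1/10) = 4σ²/30.
- Covariance, from the shared S1 samples: σ²(1 − ρ)/30.
- Correlation: (1 − ρ)/√(8(1 − ρ)) = √((1 − ρ)/8).

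This gives 0.354 at ρ = 0, 0.250 at 0.5, 0.158 at 0.8 and 0.112 at 0.9. It would be zero if the two steps were independent.

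**Confirmation of chance selections.** The table gives the simulated probability that a feature null in both parts, having passed one part 1 contrast, also reaches two-sided p < 0.05 in part 2. The independent rate is 5%. Assumptions not in the protocol: ρ, the part 2 level of 0.05, and normal log intensities with equal variances.

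| ρ | part 1 p < 0.05 | p < 5e-4 (FDR-type) | p < 1e-5 |
|---|---|---|---|
| 0 | 11.8% | 24.2% | 33.7% |
| 0.5 | 8.3% | 13.9% | 17.9% |
| 0.7 | 7.0% | 10.1% | 12.2% |
| 0.8 | 6.3% | 8.4% | 9.7% |
| 0.9 | 5.7% | 6.6% | 7.2% |

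Over the whole table the ratio to nominal runs from 5.7/5 = 1.1 to 33.7/5 = 6.7. Nearly all the excess has the PMs departing from the NM-RM-UM baseline in the same direction as the drug session.

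**Full pipeline check.** With 5000 features, 100 true effects, both part 1 contrasts and Benjamini-Hochberg at an assumed 5%, the effective threshold was about 1e-3. Chance selections were confirmed in about 18% (ρ = 0), 11% (ρ = 0.5) and 6% (ρ = 0.8). With 30% of part 2 variance as independent re-measurement error at ρ = 0.5, the rate was about 10%. With independent controls it was about 4-5%.

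**How many features.** At 1e-5, 5000 × 1e-5 = 0.05 chance selections are expected per contrast, so at most 0.05 × 0.337 ≈ 0.02 are falsely confirmed. In the Benjamini-Hochberg runs there were 11.55, 10.53 and 9.38 chance selections per trial at ρ = 0, 0.5 and 0.8. Falsely confirmed: 11.55 × 0.18 ≈ 2.1, 10.53 × 0.114 ≈ 1.2 and 9.38 × 0.056 ≈ 0.5. At a nominal 5% the figures would be about 0.6, 0.5 and 0.5.

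**If part 1 pools all 40.** The covariance becomes σ²(1 − ρ)(30/40 × 1/30 − 10/40 × 1/10) = 0. Simulated confirmation is then about 5%.

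**Splitting the 30.** Using 15 for selection and 15 for confirmation restores about 5%, but part 1 power at 1e-5 falls from 80.4% to 9.2%.

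**The case against.** The strongest reply is that this touches only a small class of features.

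- **Real effects through other pathways.** The likelier false biomarkers are compounds that fluvoxamine or rifampicin move by other routes; sections 5.1.2 and 5.1.3 list several other CYPs affected. For a feature with a real drug effect and no genotype effect, simulated two-sided confirmation is about 4-6%, essentially nominal. This stands. The table applies only to features null in both parts.
- **FDR control.** Section 9.2 adjusts the session contrasts, so chance selections are few. This stands, with one caveat: the primary endpoint in section 3.2 qualifies features on fold-change alone, without a p-value.
- **Induction.** A chance-high baseline makes session 3 look lower as well, whereas sections 5.1.2 and 5.1.3 expect CYP2C19 metabolites to fall under fluvoxamine and rise under rifampicin. Among doubly null features significant in both contrasts in opposite directions, simulated confirmation in the expected direction is about 2-3%, so no clear inflation (150-179 features per cell). This limits the concern, but the protocol does not make that pattern a selection rule.
- **Analysis set.** Section 9.2 does not restrict part 1 to the 30, and pooling all 40 removes the problem. True, but section 9.1 names the 30, so the protocol needs to settle it.
- **Wording.** The synopsis speaks of identification, and in vitro validation is planned. Sections 2.8 and 9.1 nevertheless use the validation label.

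A reader might infer that false biomarkers in general will be validated several times too often. The documents do not support that: they give no between-session correlation, and the excess is below twofold when that correlation is 0.8 or more at FDR-type thresholds. Nor is part 2 empty, since the PM samples are new data.

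**Conclusion.** Part 2 as described in section 9.1 is a genotype comparison in the volunteers used for selection, not an independent validation. For chance selections null in both parts, its two-sided error at 0.05 is roughly 6-24% at FDR-type thresholds and about 7-34% at 1e-5, instead of 5%.

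That range rests on an assumed between-session correlation of 0.9 down to 0, an assumed part 2 level of 0.05, and part 1 using only the 30 NM-RM-UMs. In absolute terms it amounts to about two falsely confirmed features or fewer per trial in the scenarios run. A claim that many biomarkers would be wrongly validated is not shown. What should change is what the trial may conclude from part 2.

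**What to change.** 1. In sections 2.8 and 9.1, describe part 2 as a genotype comparison, or internal confirmation, in the same volunteers.
2. State that part 1 selection uses the 30 NM-RM-UMs, if that is the intention. If all 40 are to be pooled, say so.
3. Reserve the term validated for features also supported by the recombinant-enzyme and hepatocyte work already planned in section 2.9.
4. Optionally, as a sensitivity analysis, give each part 2 feature a p-value from permuting genotype labels over the 40 volunteers, using only permutations in which that feature is again selected in part 1. This is feasible because PMs also attend all three sessions. The conditioning is essential: in simulation it gave about 2% false confirmation, whereas counting permutations that do not reselect the feature as non-exceedances gave about 60%.

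Items 1 to 3 cost only wording and a more modest claim. Item 4 costs computing time and slightly conservative p-values. None needs new samples. Splitting the 30 is not recommended, given the loss of part 1 power.
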